⁶ EKG must be performed at screening and on Day 1 of every cycle. Echocardiogram must be completed at screening, C2D1, and every 3 cycles thereafter (i.e. C5D1, C8D1, etc.) and as clinically indicated. Troponin I test and cardiology consult only if clinically indicated.

⁷ HIV, Hepatitis B and C serology. If screening serology results indicate potential HBV or HCV infection, viral load will be tested before starting investigational agents. TB testing will be performed only if clinically indicated.

⁸ Biochemical Profile: electrolytes, BUN, creatinine, AST, ALT, total and direct bilirubin, calcium, phosphorus, albumin, magnesium.

⁹ Pregnancy test for female participants of childbearing potential (serum or urine; if urine is positive it must be confirmed with serum test

Abbreviated Title: Trametinib and HCQ in BTC

Version Date: 04/06/2022

¹⁰ CT scan of chest, abdomen and pelvis (or MRI of chest, abdomen and pelvis if clinically indicated) every 8 (+/-1) weeks after start of study therapy. If patient taken off treatment for reason other than progression, CT scans will continue until progression or 5 months have passed since the start of study therapy whatever comes earlier. MRI of brain can be done at screening if clinically indicated.

¹¹ Mandatory tumor biopsies will be performed at baseline and any day during week 3 of cycle 2. If patient disease progresses before this, post-treatment biopsy might be performed per PI discretion at the time of progression.

¹² On Day 1 of cycles 1-4, then every 12 weeks until PD

¹³ +/- 1 week

¹⁴ After Safety Follow Up visit, subjects will be followed for adverse events by phone call or e-mail at 60 (+/- 14 days) and 90 (+/- 14 days) days. After that every 6 (\pm 1) months by phone call or e-mail for survival. If patient is taken off treatment for reason other than disease progression before 5 months have passed since the start of study therapy, we will continue to invite patient every 8 (+/-1) weeks for imaging studies until disease progression or 5 months have passed since the start of study therapy whatever comes earlier. Outside scans are acceptable.

¹⁵ If patients are not willing to come to the NIH Clinical Center, they may be followed by phone call or e-mail.

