3.6.1 Criteria for Removal from Protocol Therapy

- Participant requests to be withdrawn from active therapy
- Unacceptable toxicity (both drugs) as described in Section [3.3](#)
- PI discretion
- Positive pregnancy test or intent to become pregnant
- Drugs become unavailable
- Initiation of therapy that prevents further administration of study treatment
- Confirmed disease progression based on radiographic progression per RECIST 1.1.
- Permanent loss of capacity to consent, per requirements of section [12.3](#)

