4.1 Prohibited Therapy

The following medications are not permitted to be taken concurrently with study therapy.

- Any other anti-cancer systemic therapy.
- Other investigational agents.
- Any live vaccines (Inactivated vaccines are allowed).
- The following QT prolonging agents: mesoridazine, thioridazine, pimozide, terfenadine, cisapride, sparfloxacin, saquinavir, ziprasidone, dronedarone, piperaquine, amisulpride (Other agents with the possibility of QT prolongation should be used with caution).
- Non-steroid anti-inflammatory medications (i.e. naproxen, ibuprofen, piroxicam, diclofenac, meloxicam).
- Anti-platelet agents (i.e. clopidogrel, prasugrel, dipyridamole).
- Serotonin reuptake inhibitors (SSRIs) should be used with caution.
- Tamoxifen.

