10.2 Sample Size Determination

The primary objective of this study is to determine in a preliminary, limited size trial whether trametinib in combination with HCQ is associated with a 5-month progression free probability, which exceeds 25% when used to treat patients with cholangiocarcinoma.

Based on our analysis of data from previous trials of patients with similar eligibility requirements the median progression free survival in BTC is 2.5 months[8]. This translates to 25% without progressive disease at 5 months following an exponential failure model. Based on these results, it would be useful to demonstrate whether trametinib in combination with hydroxychloroquine is able to be associated with a median PFS of 5 months, which would correspond to 50% of patients having stable disease at 5 months. The trial will be conducted using a two-stage optimal design [52]. In order to attempt to determine if the agent offers any improvement, using alpha=0.10 and beta =0.10 as acceptable error probabilities, the trial will target 50% as the desirable proportion of patients who are still without progression at the five-month evaluation ($p_1=0.50$), and will be considered inadequate if only a fraction consistent with 20% are without progression by the same evaluation time ($p_0=0.20$).

Initially, 10 patients will be enrolled and evaluated for progression. Enrollment will be temporarily halted after the 10th patient has been accrued, unless we know that 3 patients have passed the 5-month point without progression. If 3 or more of the first 10 patients enrolled have not progressed at the 5-month evaluation, then accrual will continue until a total of 17 patients have been entered. If, among the first 10 patients accrued, 0 to 2 are able to be progression-free at the 5-month evaluation, then no further patients will be enrolled after such a determination has been made. If 6 or more of the total cohort of 17 patients have been found to be progression-free at 5 months, then this will indicate an adequate progression free probability to justify further consideration of trametinib in combination with hydroxychloroquine in this population of patients. On the other hand, if 3 to 5 of 17 are progression-free at 5 months, this will be considered insufficient. Under the null hypothesis (20% progression free at 5 months), the probability of being able to stop accrual after 10 patients have been evaluated at 5 months is 68%.

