10.4.2 Analysis of the Primary Endpoints

The fraction of patients who are able to not have progressive disease at 5 months will be reported along with a 95% confidence interval. A Kaplan-Meier curve of PFS will also be created and reported along with the 5-month PFS probability and its 95% confidence interval.

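### By default, a patient who stops study drugs without progression, starts another anti-cancer therapy and is alive and progression-free at 5 months counts as a success of trametinib plus HCQ

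*Combined protocol and SAP*

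**What the plan says.** - **Imaging after stopping.** Section 3.4, footnote 10: "If patient taken off treatment for reason other than progression, CT scans will continue until progression or 5 months have passed since the start". Footnote 14 says the same in terms of inviting the patient for scans every 8 weeks. Neither footnote ends when a new therapy begins.
- **Leaving treatment and leaving the study.** Section 3.6.1 lists several exits other than progression: participant request, toxicity, PI discretion and "Initiation of therapy that prevents further administration of study treatment". Section 3.6.2 does not make a new therapy a reason to leave the study.
- **Other anti-cancer therapy.** Section 4.1 includes it in a list that opens "The following medications are not permitted to be taken concurrently with study therapy". The bar does not reach past the last dose.
- **Events and population.** PFS, defined at the end of section 6.3.3.5, has two events: progression and death. Section 10.3 puts everyone with at least one dose of both agents in the efficacy evaluation.
- **Primary summary.** Section 10.4.2 reports "The fraction of patients who are able to not have progressive disease at 5 months" with a 95% confidence interval, plus a Kaplan-Meier curve of PFS.
- **Decision rule.** Section 10.2 continues past 10 patients if at least 3 are progression-free at 5 months, and calls the result adequate if at least 6 of 17 are.

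**The concern.** The trial asks whether the combination beats a benchmark. If a patient leaves the study drugs without progression, starts a different cancer treatment and is still progression-free at 5 months, part of that result may belong to the new treatment. A randomised comparison would have a control arm in which similar switching could occur. Here the count is set against a fixed rate, so any gain from the new therapy pushes in one direction, towards declaring success. With cut-offs of 3 of 10 and 6 of 17, one such patient can change either decision.

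The silence matters as well. Section 10.2 allows for unevaluable patients but does not define them. The same patient could therefore be counted or dropped after the outcome is known.

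**Working it through.** **Inputs from section 10.2.** The error rates: "using alpha=0.10 and beta =0.10 as acceptable error probabilities". The target: "the trial will target 50% as the desirable proportion of patients who are still without progression at the five-month evaluation", so p1 = 0.50. The null: the result "will be considered inadequate if only a fraction consistent with 20% are without progression", so p0 = 0.20. Stage 1 has 10 patients, continuing on 3 or more. The final rule is 6 or more of 17. The stated probability of stopping at stage 1 under the null is 68%.

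**Step 1: reproduce the design.** With X1 ~ Bin(10, p) and X2 ~ Bin(7, p):

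- P(stop at stage 1) = P(X1 ≤ 2)
- P(declare success) = Σ over x1 = 3…10 of P(X1 = x1) · P(X2 ≥ 6 − x1)

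At p = 0.20, P(stop) = 0.678, which matches the stated 68%, and P(success) = 0.094. At p = 0.50, P(success) = 0.904. The design is correct as stated.

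**Step 2: let switchers count as successes when progression-free.** Let s be the share of all patients who switch before progression and q their chance of being progression-free at 5 months. The documents give neither. The effective rate at a true 20% is p* = (1 − s)·0.20 + s·q.

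| s | q | p* | P(stop at 10) | P(success) |
|---|---|---|---|---|
| 0 | – | 0.200 | 0.678 | 0.094 |
| 5% | 0.25 | 0.2025 | 0.670 | 0.099 |
| 10% | 0.25 | 0.205 | 0.663 | 0.104 |
| 20% | 0.25 | 0.210 | 0.647 | 0.114 |
| 5% | 0.50 | 0.215 | 0.632 | 0.124 |
| 10% | 0.50 | 0.230 | 0.586 | 0.159 |
| 20% | 0.50 | 0.260 | 0.496 | 0.241 |

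**Step 3: what a large inflation requires.** The net gain is p* − 0.20 = s·(q − 0.20). A gain of 3 percentage points (P(success) = 0.159) needs s = 0.03/0.30 = 10% when q = 0.50, or 0.03/0.05 = 60% when q = 0.25. A gain of 5 points (P(success) = 0.212) needs 0.05/0.30 = 17%, or 0.05/0.05 = 100%.

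**Step 4: a case tied to the plan's own benchmark.** Section 10.2 says "the median progression free survival in BTC is 2.5 months". Assume constant hazards, a switch at 2 months, and a new therapy with that 2.5-month median. A patient progression-free at 2 months stays so to 5 months with probability 0.5^(3/2.5) = 0.435 on the new therapy. At the null rate without switching, the probability is 0.20^(3/5) = 0.381. The gain per switcher is 0.435 − 0.381 = 0.054. P(success) becomes 0.099, 0.105 and 0.116 for s = 5%, 10% and 20%. If the new therapy instead had a 5-month median, 0.5^(3/5) = 0.660, and s = 10% gives 0.154.

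**Step 5: count switchers as failures.** The effective rate is (1 − s)·p if each switcher would otherwise have had success rate p.

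| s | P(success) at p = 0.20 | Power at p = 0.50 |
|---|---|---|
| 0 | 0.094 | 0.904 |
| 5% | 0.077 | 0.867 |
| 10% | 0.062 | 0.820 |
| 20% | 0.037 | 0.697 |

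**The case against.** **The plan never says that switchers are successes.** True. It follows from silence in the PFS definition and sections 10.3 and 10.4.2, so the point is stated as a default. Nor is imaging to 5 months assured: footnote 14 is an invitation, footnote 15 allows telephone or e-mail follow-up, and patient request or PI discretion can end participation.

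**Section 3.6.1 does not say anti-cancer therapy.** True. A reader might infer that the plan expects patients to switch to another cancer drug. The text does not support that: a needed drug from the section 4.1 list, such as an NSAID or an antiplatelet agent, fits the criterion equally well. The point does not depend on that line, because the other exits also leave a patient off study drugs, without progression and free to start something else.

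**The effect may be small.** This stands in part. Section 1.2.1 says there is no standard second-line option, and section 3.1 lets a patient continue one drug when the other is stopped for toxicity. The only discontinuation rate cited is 9%, for trametinib alone (section 1.2.5.3), and not all such patients would switch before progression. A reader might take 0.16 or 0.21 as the expected type I error. Step 3 shows that this needs frequent switching, an effective new therapy, or both.

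**Following everyone regardless of later therapy is a legitimate estimand and avoids informative censoring.** This stands. It should then be a stated choice. Whether it matches the benchmark depends on how the trials behind the historical rate handled new therapy, which the documents do not show.

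**Conclusion.** The gap is real. No rule covers anti-cancer therapy started before progression, and the rules as written credit the combination with any such patient who is alive and progression-free at 5 months. To the extent that the new therapy improves on what would have happened without it, the bias favours a positive result, and a single-arm design cannot remove it.

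Its size cannot be estimated from the documents. At a true 20% rate, type I error rises from 0.094 to 0.099–0.114 for 5–20% switching with q = 0.25, and to 0.124–0.241 with q = 0.50. A new therapy performing at the protocol's 2.5-month median gives 0.099–0.116. Values of 0.16 or 0.21 require a net gain of 3 or 5 percentage points.

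The sample size and the 68% stopping probability are correct. Continued scanning after treatment stops is sound and is not the fault. The change is worth making before outcomes are known because it fixes the meaning of a count on which both decisions turn.

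**What to change.** 1. In section 10.4.2, state that starting any new anti-cancer therapy before progression and before the 5-month assessment counts as not progression-free in the primary count, at both stages.
2. Report the count regardless of new therapy as a sensitivity analysis.
3. State the matching handling for the Kaplan-Meier PFS and its 5-month estimate, so that the two primary summaries do not follow different rules.
4. Record the start date of any new anti-cancer therapy during follow-up. The study calendar lists concomitant medications only at screening, baseline and Day 1 of each cycle.

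Keep the scans, N = 17 and both cut-offs.

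The cost is a short addition to the text, one data field and one extra tabulation, plus some power. Type I error stays at or below 0.094. Power at 50% falls from 0.904 to about 0.867 or 0.820 if 5% or 10% of patients switch and would otherwise have had the 50% success rate. That is below the planned 0.90 and should be acknowledged. A patient who stops for toxicity and switches while still controlled is counted against the combination; the sensitivity count shows how much this matters.

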3.5 Costs and Compensation

3.5.1 Costs

NIH does not bill health insurance companies or participants for any research or related clinical care that participants receive at the NIH Clinical Center. If some tests and procedures performed outside the NIH Clinical Center, participants may have to pay for these costs if they are not covered by insurance company. Medicines that are not part of the study treatment will not be provided or paid for by the NIH Clinical Center.

3.5.2 Compensation

No compensation is offered on this study.

3.5.3 Reimbursement

The NCI will cover the costs of some expenses associated with protocol participation. Some of these costs may be paid directly by the NIH and some may be reimbursed to the participant/guardian as appropriate. The amount and form of these payments are determined by the NCI Travel and Lodging Reimbursement Policy.

3.6 Criteria for Removal from Protocol Therapy

Prior to removal from the study, effort must be made to have all subjects complete a safety visits approximately 30 days following the last dose of study therapy.

3.6.1 Criteria for Removal from Protocol Therapy

- Participant requests to be withdrawn from active therapy
- Unacceptable toxicity (both drugs) as described in Section [3.3](#)
- PI discretion
- Positive pregnancy test or intent to become pregnant
- Drugs become unavailable
- Initiation of therapy that prevents further administration of study treatment
- Confirmed disease progression based on radiographic progression per RECIST 1.1.
- Permanent loss of capacity to consent, per requirements of section [12.3](#)

3.6.2 Off Study Criteria

- Death
- Patient request to be withdrawn from study
- PI discretion
- Lost to follow up
- PI decision to end the study
- Screen failure.

3.6.3 Lost to Follow-up

A participant will be considered lost to follow-up if he or she fails to return for 3 scheduled visits and is unable to be contacted by the study site staff.

The following actions must be taken if a participant fails to return to the clinic for a required study visit:

- The site will attempt to contact the participant and reschedule the missed visits and counsel the participant on the importance of maintaining the assigned visit schedule and ascertain if the participant wishes to and/or should continue in the study.
- Before a participant is deemed lost to follow-up, the investigator or designee will make every effort to regain contact with the participant (where possible, 3 telephone calls and, if necessary, an IRB approved certified letter to the participant's last known mailing address or local equivalent methods). These contact attempts should be documented in the participant's medical record or study file.
- Should the participant continue to be unreachable, he or she will be considered to have withdrawn from the study with a primary reason of lost to follow-up

4 CONCOMITANT MEDICATIONS/MEASURES

All routine and appropriate supportive care (including blood products) will be provided during this study, as clinically indicated, and in accordance with the standard of care practices. Clinical judgment should be utilized in the treatment of any adverse event experienced by the patient.

4.1 Prohibited Therapy

The following medications are not permitted to be taken concurrently with study therapy.

- Any other anti-cancer systemic therapy.
- Other investigational agents.
- Any live vaccines (Inactivated vaccines are allowed).
- The following QT prolonging agents: mesoridazine, thioridazine, pimozide, terfenadine, cisapride, sparfloxacin, saquinavir, ziprasidone, dronedarone, piperaquine, amisulpride (Other agents with the possibility of QT prolongation should be used with caution).
- Non-steroid anti-inflammatory medications (i.e. naproxen, ibuprofen, piroxicam, diclofenac, meloxicam).
- Anti-platelet agents (i.e. clopidogrel, prasugrel, dipyridamole).
- Serotonin reuptake inhibitors (SSRIs) should be used with caution.
- Tamoxifen.

5 CORRELATIVE STUDIES FOR RESEARCH

5.1 Biospecimen Collection

A description of correlative studies including a brief statement of rationale and processing information is made below.

Test/assay	Sample volume (approx.)	Type of tube/ tissue sample ^a	Collection point	Location of specimen analysis
Blood Samples				
Immune-monitoring by FACS	Blood, 100 ml	EDTA (Purple top tubes)	See Study Calendar 3.4	BPC ([name] Lab)
Serum p62 by ELISA	4 ml	SST tube	See Study Calendar 3.4	BPC ([name] Lab)
Whole exome/panel	Blood, 2.5 mL	1 PAX gene DNA tube	See Study Calendar 3.4	BPC ([name] Lab)
Tumor Samples				
IHC for immune cell infiltration	Tumor sample		At time of biopsies	Laboratory of Pathology
RNA seq	Tumor sample		At time of biopsies	Laboratory of Pathology
Whole exome/panel	Tumor sample		At time of biopsies	Laboratory of Pathology
Proteomics	Tumor sample		At time of biopsies	[name] Laboratory
Metabolomics	Tumor sample		At time of biopsies	[name] Laboratory
RNA Nanostring analysis	Tumor sample		At time of biopsies	[name] Laboratory
IHC	Tumor sample		At time of biopsies	[name] Laboratory
a. Please note that tubes and media may be substituted based on availability with the permission of the PI or laboratory investigator.				

5.1.1 Correlative studies of blood samples

Blood samples will be collected at time points indicated in the Study Calendar. Blood samples will be initially sent to the Blood Processing Core (BPC) for barcoding, storage and analysis.

5.1.1.1 Immune monitoring

We will analyze PBMC for quantitative and functional changes of effector cells by FACS. The effect on (i) CD4 T cell number and activity, (ii) CD8 T cell number and activity, (iii) NK cell number and activity, (iv) Treg number, (v) MDSC: frequency + functional assay, and (vi) the detection of tumor-associated antigens using tetramer assay. These data will provide further

information in terms of potential immune modulation effect with the combination therapy of trametinib/HCQ. These experiments will be done in BPC.

5.1.1.2 Serum p62 level

We predict that p62 levels may be elevated in serum with treatment as this has been demonstrated to be a biomarker for impaired autophagy [51]. We will test this hypothesis by obtaining blood samples from patients during routine blood collection and utilizing a commercially available ELISA assay to determine the concentration of p62 in the bloodstream. This study may also lead to a predictive biomarker for response to trametinib plus HCQ. These experiments will be done in BPC.

5.1.2 Tumor studies (non-genetic analysis)

Mandatory tumor biopsies will be performed at baseline and anytime during week 3 of Cycle 2. If patient disease progresses before week 3 of Cycle 2, post-treatment biopsy might be performed per PI discretion at the time of progression. It is preferred that at **least two core biopsies ≥18 gauge in diameter and ≥1 cm in length** will be obtained.

5.1.2.1 IHC

IHC will be performed on tumor tissue for assessment of immune cell infiltration (e.g. CD3+ CD4/8 cells, PDL1 etc.). Immunohistochemistry will be performed in the Laboratory of Pathology under the direction of [name].

5.1.2.2 Omics study

Tumor samples will be collected for proteomics and metabolomics studies to investigate the differential expression of protein and metabolite that might be associated with the treatment outcome or efficacy. These experiments will be done in [name] lab.

5.2 Samples for Genetic/Genomic Analysis

5.2.1 KRAS evaluation

KRAS mutation detection will be formed with TruSight™ Oncology 500 panel in Lab of Pathology.

5.2.2 RNA Nanostring analysis

Tumor samples will be used for gene expression profiling with Nanostring analysis (nCounterPan Cancer Immunology Profile) in BPC.

5.2.3 Whole exome/Panel (tumor/normal) and RNAseq (tumor)

Whole exome will be done on tumor and blood sample. RNAseq will be done on tumor for expressed somatic mutations and neoantigen discovery. Tumor material for these analyses will be sent to the Laboratory of Pathology, the laboratory of Drs. [name] and [name] (NCI Genetics Branch). Specifically, the expression of different signaling pathway, including interferon gamma signaling, immune cell functional molecular, e.g. perforin and granzyme, will be investigated

5.2.4 Management of Results

Subjects will be contacted if a clinically actionable gene variant is discovered. Clinically actionable findings for the purpose of this study are defined as disorders appearing in the

American College of Medical Genetics and Genomics recommendations for the return of incidental findings that is current at the time of primary analysis. (A list of current guidelines is maintained on the CCR intranet: <https://ccrod.cancer.gov/confluence/display/CCRCRO/Incidental+Findings+Lists>). Subjects will be contacted at this time with a request to provide a blood sample to be sent to a CLIA certified laboratory. If the research findings are verified in the CLIA certified lab, the subject will be offered the opportunity to come to NIH (at our expense) to have genetic education and counseling to explain this result. If the subject does not want to come to NIH, a referral to a local genetic healthcare provider will be provided (at their expense).

This is the only time during the course of the study that incidental findings will be returned. No interrogations regarding clinically actionable findings will be made after the primary analysis.

